7.2 Assessment types

7.2.1 Safety assessments

Safety will be monitored by assessing (*Vital sign laboratory test result, ECG etc*) as well as collecting of the adverse events at every visit. For details on AE collection and reporting, refer to [Section 8](#).

7.2.1.1 Physical examination

A complete physical examination will include the examination of general appearance, skin, neck (including thyroid), eyes, ears, nose, throat, lungs, heart, abdomen, back, lymph nodes, extremities, vascular and neurological. If indicated based on medical history and/or symptoms, rectal, external genitalia, breast, and pelvic exams will be performed.

Physical examinations should be symptom driven after the Screening Visit.

Ophthalmological examinations will be performed by an ophthalmologist at screening, at each visit of C1, day 1 of C2, then day 1 of every 2 cycles.

Significant findings that were present prior to the signing of informed consent must be included in the Medical History page on the patient's CRF. Significant new findings that begin or worsen after informed consent must be recorded on the Adverse Event page of the patient's CRF.

7.2.1.2 Vital signs

Vital sign exam is detected at pre-dose, and 2h, 4h, after dose in C1D1, and C1D15, and be detected pre-dose in other setting time points.

Vital signs include pulse/heart rate, respiratory rate, temperature, blood pressure measurements. After the patient has been sitting for five minutes, with back supported and both feet placed on the floor, systolic and diastolic blood pressure will be measured with an appropriately sized cuff. If the result is abnormal, repeat the measurement or change the instrument measurement to confirm. The repeat sitting measurements will be made at 1-2 minute intervals. In case the cuff sizes available are not large enough for the patient's arm circumference, a sphygmomanometer with an appropriately sized cuff may be used.

7.2.1.3 Height and weight

Height in centimeters (cm) and body weight (to the nearest 0.1 kilogram [kg] in indoor clothing, but without shoes) will be measured. (Note: CRFs are designed to collect the data in the units they are measured in; e.g., height in cm or in and weight in kg). See

Item	Section	Screening period		Study treatment period							Follow up period		
		0 molecu lar screeni ng	1 Screening	Cycle 1 Day 1 through 21			Cycle 2 Day 22 through 42			Cycle 3-X 21d/cycle, visit on 1st day of every 2 cycles	End of treatment visit (EOT)/early discontinuation (Section 7.1.4)	Safety follow up	Progress Disease follow up
Day			-28 to -1	1 ± 0	8 ± 1	15 ± 1	22 ± 1	29 ± 3	36 ± 3	43 ± 3	N/A	+ 7	± 7
molecular agent (Phase I and Phase II agent)	7.1.1	X											
consent	7.1.2		X										
exclusion criteria	5.2, 5.3		X										
detection	7.1.1	X1	X										
oratory/tumor treatment history	7.1.2.2		X2	X	X	X	X	X	X	X			
agnosis and activity	7.1.2.2		X										
nitant treatment	7.1.2.2		X	X	X	X	X	X	X	X		X	
raphy	7.1.2.2		X										
amination	7.2.1.1		X	X	X	X	X	X	X	X			
ight (cm)	7.2.1.3		X										
ight (kg)	7.2.1.3		X	X			X			X	X		
G	7.2.1.4		X	X	X	X	X	X	X	X	X		
signs	7.2.1.2		X	X6	X	X6	X	X	X	X	X		
ogy exam	7.2.1.1		X	X	X	X	X			X	X		
cy test	7.2.1.5		X	X3			X4			X4	X4		
lispensed	6.6.3			X	X	X	X	X	X	X			
ministration	6.1.1			X5	X	X	X	X	X	X			

ame	Protocol Section	Screening period		Study treatment period							follow up period	
		0 molecule	lar screeni	Cycle 1 Day 1 through 21			Cycle 2 Day 22 through 42			Cycle 3-X 21d/cycle, visit on 1st day of every 2 cycles	End of treatment visit (EOT)/early discontinuation (Section 7.1.4)	Safety follow up
Day		-28 to -1	1 ± 0	8 ± 1	15 ± 1	22 ± 1	29 ± 3	36 ± 3	43 ± 3	N/A	+ 7	± 7
treatment and survival	7.1.5										X	X
eval	7.1.5.2											

, [错误!未找到引用源。](#)

7.2.1.4 Eastern Cooperative Oncology Group Performance

ECOG performance scores ([Appendix 14.2](#)) will be assessed within 14 days prior to the first dose and subsequent visits including the SFUV.

7.2.1.5 Laboratory evaluations

Laboratory tests include blood routine, blood biochemistry, urine tests, thyroid function, and coagulation. If the results of within 7 days before C1D1 are judged to be normal by the investigator, the blood routine, blood biochemistry, urine test, and coagulation function of C1D1 may be waived; if the thyroid function test C1D1 can be provided within 28 days by the regular medical institution issued, and there is no abnormal report on the thyroid function test with normal range, the C1D1 examination can be exempted. After Cycle 2, clinical chemistry (to include calcium and inorganic phosphorus), hematology may be performed once per cycle or more frequently at the investigator's discretion.

Hematology: red blood cell count, hemoglobin, hematocrit, reticulocyte count, neutrophil, lymphocyte, eosinophil, mononuclear cell, basophil, platelet count.

Blood chemistry including LFTs and KFTs: LFTs include total protein, albumin, total and direct bilirubin, ALT, AST, gamma-glutamyl transferase, creatine phosphokinase (CK/CPK), alkaline phosphatase and lactate dehydrogenase; KFTs include blood urea nitrogen, creatinine and uric acid; other blood chemistry includes blood glucose, chloride, sodium, potassium, calcium, phosphate, amylase, and lipase, lactate dehydrogenase (LDH), CKMB (Creatine Kinase MB Isoenzyme).

Coagulation function tests: prothrombin time (PT), activated partial prothrombin time (APTT) and international normalized ratio (INR);

Serum virology: HBV, HCV, and HIV. If HCV antibody test result is positive, HCV RNA test should be conducted, and HBsAg antigen positive patients should be tested for HBV DNA level.

Thyroid: T3 [free], T4 [free], TSH

Urinalysis: gravity, protein, glucose and blood will be performed. Any significant findings on dipstick will be followed up with a microscopic evaluation where WBC and RBC sediments will also be measured.

Blood samples for hematology, blood chemistry and coagulation tests, and urine samples for urinalysis will be collected according to the schedule shown in [Table 7-1](#) , [Table 7-2 and Table 7-3](#).

Blood sampling for viral serology will be performed at screening for detection of HBV, HCV, and HIV according to local practice.

Pregnancy assessment: For child-bearing potential patients: Pregnancy test for pregnancy is performed on C1D1, C2D1, and every 2 cycles from Cycle 3 when applicable. Serum pregnancy test is mandatory at screening visit. After screening and baseline, urine pregnancy test which if positive, confirm with serum test. Whereas serum pregnancy test is required at EOT visit. If needed, Serum HCG (β -HCG) will be examined.

Clinical laboratory tests will be reviewed for results of potential clinical significance at all time points throughout the study. The Investigator will evaluate any change in laboratory values. If the Investigator determines a laboratory abnormality to be clinically significant, it is considered a laboratory AE; however, if the abnormal laboratory value is consistent with a current diagnosis, it may be documented accordingly.

Cardiac function test: Troponin will be measured at screening. And any indication of abnormalities may result in further investigations.

7.2.1.6 Echocardiogram or MUGA (multiple gated acquisition) scan

Left ventricular ejection fraction (LVEF) should be measured at screening, at the investigator's discretion if there are signs or symptoms of cardiotoxicity during the study, and at the SFUV.

LVEF can be measured via echocardiogram or MUGA scan. A delegated qualified staff should be responsible for LVEF measurement. LVEF must be within normal range.

7.2.1.7 12-lead Electrocardiogram

A standard 12-lead ECG will take place on screening and subsequent visits. Patients should be supine for 5 minutes prior to the ECG. ECGs will be obtained prior to dosing(-60min), one hour post-dose(\pm 20min), three hours post-dose(\pm 30min), four hours post-dose(\pm 30min), and eight hours post-dose(\pm 60min) on Cycle 1 Day 1 and Cycle 2 Day 1. ECG measurement timepoints will

match PK sampling timepoints, ECG measurement must be taken within 15 min before PK sampling at each time points. The timepoints may be modified when the PK data (HH2710 and selected metabolites) in humans is available.

Standard ECG parameters, including heart rate, QRS, PR, RR, QT, and the QT interval corrected for heart rate using Frederica's formula will be measured.

ECG trace report will be collected and archived at patient chart and study file respectively.

Interpretation of the tracing must be made by a qualified physician and documented on the ECG CRF page. Each ECG tracing should be labeled with the study number, patient initials (where regulations permit), patient number, date, and kept in the source documents at the study site. Clinically significant abnormalities present when the patient signed informed consent should be reported on the Medical History CRF page. Clinically significant findings must be discussed with Haihe prior to enrolling the patient in the study. New or worsened clinically significant findings occurring after informed consent must be recorded on the Adverse Events CRF page.

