7.2.2 Pharmacokinetics

7.2.2.1 Blood sample schedule

Study drug will be taken QD at cycle1 day 1 and twice daily from the second day of cycle 1 in the first 3 patients. First dose in clinic on days when PK sampling occurs i.e., Cycle 1 Day 1 and Cycle 1 Day15, remaining doses on all other days to be self-administered by patient.

In order to detect PK of a single administration, for the first 3 patients, a single administration will be given on the first day, administration twice daily from the second day. Patients will undergo serial blood sampling 2ml for PK analysis during cycle 1 on day 1 at pre-dose and 15min, 30min, 1, 2, 3, 4, 6, 8 hours post-dose, and 12 hours post-dose (if available); on day 2 at pre-dose; on cycle1 day 7 (pre-dose), cycle1 day 10 (pre-dose), day 15 at pre-dose and 15min, 30min, 1, 2, 3, 4, 6, and 8 hours post-dose, and 12 hours post dose (if available); and day 16 at pre-dose. On day 22, prior to dose administration, a final blood sample was collected for pharmacokinetic analyses. See [Table 7-2](#), [错误!未找到引用源。3](#).

Serial blood samples will be collected from all patients to assess single dose and multiple dose plasma PK of HH2710 and its metabolite. PK parameters will be derived from each individual plasma concentration-time profiles. Refer to [Section 10.6.4](#) for list of PK parameters that will be estimated.

PK blood sample collection and handling

Blood samples will be taken by either direct venipuncture or an indwelling cannula inserted in a forearm vein. At specified time points described in [Table 7-2](#) and [错误!未找到引用源。3](#), 2 mL blood draws will be collected into tubes containing K2 EDTA and gently inverted several times to thoroughly mix the anticoagulant. Tubes will be centrifuged to separate plasma and plasma will

immediately be transferred into labeled 2 mL polypropylene screw-cap tubes. Plasma samples will be placed in a freezer in an upright position until shipment to the bioanalytical laboratory for analysis.

All sampling is relative to the ingestion of HH2710. On days and time points where blood PD samples are to be drawn, the PK sample must be drawn first. The exact collection date and time of all samples must be documented on the PK blood collection CRF pages. The date and exact time of dosing, as well as the date and actual time of blood sampling must be recorded on the CRF.

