Refer to the [HH2710-G101 Laboratory Manual] for detailed instructions for the collection, handling, and shipment of PK samples.

Intensive PK sampling will be done in the dose escalation portion of the trial. Additional PK sampling will be drawn every two cycles prior to Day 1 dosing in all patients in the dose escalation between Cycle 1 to Cycle 9 (e.g. Cycle 3 Day 1, Cycle 5 Day 1, Cycle 7 Day 1, Cycle 9 Day 1) ([Table 7-2](#)).

PK samples at pre-dose, 2h, 4h, a 6h, 8h, and 24h post dose will also be obtained at Cycle 1 Day 1 and Cycle 1 Day 15 for patients in the Phase I dose expansion stage and Phase II portions of the trial ([Table 7-3](#)).

Table 7-2: PK blood sampling time for Phase I dose escalation stage

CxDx	C1D1	C1D1	C1D1	C1D1	C1D1	C1D1	C1D1	C1D1	C1D1	C1D2	C1D7	C1D10	C1D15	C1D15	
No.	1	2	3	4	5	6	7	8	9	10	11	12	13	14	15
Time	pre-dose	15min	30min	1h	2h	3h	4h	6h	8h	12h (If available)	24h (pre-dose)	pre-dose	pre-dose	pre-dose	15min
Window (min)	-30	±5	±5	±5	±10	±10	±10	±30	±30	±60	-30	-30	-30	-30	±5
Blood Sampling	2mL	2mL	2mL	2mL	2mL	2mL	2mL	2mL	2mL	2mL	2mL	2mL	2mL	2mL	2mL
CxDx	C1D15	C1D15	C1D15	C1D15	C1D15	C1D15	C1D15	C1D15	C1D16	C2D1	C3D1	C5D1	C7D1	C9D1	NA
No.	16	17	18	19	20	21	22	23	24	25	26	27	28	29	NA
Time	30min	1h	2h	3h	4h	6h	8h	12h (If available)	pre-dose	pre-dose	pre-dose	pre-dose	pre-dose	pre-dose	NA
Window(min)	±5	±5	±10	±10	±10	±30	±30	±60	-30	-30	-30	-30	-30	-30	NA

Blood Sampling	2mL	NA											
----------------	-----	-----	-----	-----	-----	-----	-----	-----	-----	-----	-----	-----	----

Table 7-3: PK blood sampling time for Phase I dose expansion stage and Phase II

CxDx	C1D1	C1D1	C1D1	C1D1	C1D1	C1D2	C1D15	C1D15	C1D15	C1D15	C1D15	C1D15
No.	1	2	3	4	5	6	7	8	9	10	11	12
Time	pre-dose	2h	4h	6h	8h	24h	pre-dose	2h	4h	6h	8h	24h
Window(min)	-30	±10	±10	±30	±30	±60	-30	±10	±10	±30	±30	±60
Blood Sampling	2mL	2mL	2mL	2mL	2mL	2mL	2mL	2mL	2mL	2mL	2mL	2mL

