10.6.4 Pharmacokinetic Analysis

Samples for PK analysis of HH2710 and its metabolite will be obtained from all patients enrolled in Phase I dose escalation/expansion and Phase II trial.

Below is the list of PK parameters that will be calculated after single dose (C1D1) and steady State (C1D15).

Table 10-2 PK Parameters Description

PK Parameter (plasma)	Description
C _{max}	Peak plasma concentration determined manually by visual inspection of plasma concentration vs. time figures on the untransformed (linear) scale of measurement
t _{max}	Time to reach the peak plasma concentration determined manually by visual inspection of plasma concentration vs. time figures on the untransformed (linear) scale of measurement
AUC ₀₋₂₄	Area under the plasma concentration-time curve from 0 to 24 hours post-dose, calculated by linear/log trapezoidal method
AUC _{0-∞}	Area under the plasma concentration-time curve from time zero to infinity after dosing calculated by linear/log trapezoidal method
%AUC _{extrap}	Area under the plasma concentration-time curve extrapolated from time t to infinity as a percentage of total AUC (%)
Lambda _z (λ _z)	Terminal phase rate constant, determined by linear regression of at least 3 points on the terminal phase of the log-linear plasma concentration-time curve. The correlation coefficient (r ²) for the goodness of the fit of the regression line through the data points has to be 0.85 or higher for the value to be considered reliable. If the WinNonlin data points are not on the linear portion of the terminal slope, the data points will be selected manually prior to calculation of Lambda _z
t _{1/2}	Terminal half-life, defined as 0.693 (ln2) divided by Lambda z
CL/F	The apparent total body clearance of drug from the plasma (volume x time-1)
V _z /F	The apparent volume of distribution during terminal phase (associated with λ _z)(volume)

Descriptive statistics [n, arithmetic mean, standard deviation, coefficient of variation (CV), median, minimum, maximum, geometric mean, geometric standard deviation geometric CV] will be used

to summarize PK parameters by treatment. For $t_{1/2}$ and t_{max} , regular descriptive statistics and 95% confidence intervals about the arithmetic mean will be calculated, if possible, for each dose. Refer to the PK analysis plan for additional details regarding with the PK analyses.

A listing of blood PK concentrations and parameters will be provided.

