8.9 Pharmacokinetic Analysis

Pharmacokinetic parameters will be determined with non-compartmental analysis method with PK Analysis Set.

Samples for PK analysis of HH2710 and selected metabolites will be obtained from all Phase I/II patients during their first cycle of treatment (Cycle 1). PK samples will also be obtained from additional patients in Phase II depending on the outcome of initial PK analysis.

Below is the list of various PK parameters that will be calculated after Dose 1 (Day 1) and at Steady State (Day 22).

Table 2 PK parameters Description

PK Parameter (plasma)	Description
C_{\max}	Peak plasma concentration determined manually by visual inspection of plasma concentration vs. time figures on the untransformed (linear) scale of measurement

t_{max}	Time to reach the peak plasma concentration determined manually by visual inspection of plasma concentration vs. time figures on the untransformed (linear) scale of measurement
AUC_{0-12}	Area under the plasma concentration-time curve from 0 to 12 hours postdose, calculated by linear/log trapezoidal method
AUC_{0-last}	Area under the plasma concentration-time curve from time 0 to time of last observation after dosing calculated by linear/log trapezoidal method
Lambda_z (λ_z)	Terminal phase rate constant, determined by linear regression of at least 3 points on the terminal phase of the log-linear plasma concentration-time curve. The correlation coefficient (r^2) for the goodness of the fit of the regression line through the data points has to be 0.85 or higher for the value to be considered reliable. If the WinNonlin data points are not on the linear portion of the terminal slope, the data points will be selected manually prior to calculation of Lambda_z
$t_{1/2}$	Terminal half-life, defined as $0.693 / \lambda_z$
CL/F	The total body clearance of drug from the plasma (volume x time-1)
V_z/F	The apparent volume of distribution during terminal phase (associated with λ_z)(volume)

Descriptive statistics [n, arithmetic mean, standard deviation, coefficient of variation (CV), median, minimum, maximum, geometric mean, geometric standard deviation geometric CV] will be used to summarize PK parameters by treatment. For $t_{1/2}$ and t_{max} , regular descriptive statistics and 95% confidence intervals about the arithmetic mean will be calculated, for each dose.

A listing of blood PK concentrations and parameters will be provided.

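### The rule pairing serial ECGs with PK samples cannot be met for post-dose ECGs on C2D1, or for two C1D1 ECGs in expansion and Phase II, so no serial post-dose QTc-concentration pairs are scheduled at steady state

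*Protocol*

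**What the plan says.** **ECGs.** Protocol 7.2.1.7 first sets a general rule: "A standard 12-lead ECG will take place on screening and subsequent visits". It then adds a denser series, before dosing and at 1, 3, 4 and 8 hours after it, "on Cycle 1 Day 1 and Cycle 2 Day 1". ECG times are to match PK times, and "ECG measurement must be taken within 15 min before PK sampling at each time points". The section allows the times to be changed once human PK data are available. The ECG row of Table 7-1 marks an ECG at each treatment visit, including C1D15, without a time relative to dose.

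**PK sampling.** Protocol 7.2.2.1 and its tables put the serial profiles on other days.
- Escalation (Table 7-2): full profiles on C1D1 and C1D15, the second being "day 15 at pre-dose and 15min, 30min, 1, 2, 3, 4, 6, and 8 hours post-dose". For C2D1: "On day 22, prior to dose administration, a final blood sample was collected for pharmacokinetic analyses".
- Expansion and Phase II (Table 7-3): samples before dosing and at 2, 4, 6, 8 and 24 hours, which "will also be obtained at Cycle 1 Day 1 and Cycle 1 Day 15 for patients in the Phase I dose expansion stage" and in Phase II. The table has no C2D1 sample.

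**Steady-state PK.** The documents name different days. In Protocol 10.6.4 the parameters are "calculated after single dose (C1D1) and steady State (C1D15". In SAP 8.9 they are "calculated after Dose 1 (Day 1) and at Steady State (Day 22".

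**ECG analysis.** SAP 8.8.1.6 plans observed values and changes from baseline by visit, a shift table and a listing.

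**The concern.** The protocol makes the pairing mandatory but places the second ECG series on a day without a serial PK profile. A site that follows both sections cannot comply, and each unmatched ECG becomes a deviation that it could not avoid.

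The information at stake is QTc read against a concurrent concentration at steady state. ECG findings belong to the Phase I primary safety endpoint (Protocol 3). Cardiotoxicity is listed as an important potential risk (1.2.2). The drug inhibits hERG with an IC50 of 12.8 µmol/L (1.2.1.1.3). Exposure at steady state is reported as 3 to 4 times that after the first dose (2.3), so the C1D1 pairs do not cover the exposure that patients reach on continued dosing.

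**Working it through.** There is no power or error rate to reproduce here. The check matches two schedules.

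**Inputs.** ECG windows from 7.2.1.7, in minutes after dose: pre-dose -60 to 0; 1 h 40 to 80; 3 h 150 to 210; 4 h 210 to 270; 8 h 420 to 540. PK times and windows from Tables 7-2 and 7-3. C2D1 is Day 22 (Table 7-1).

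**Rule applied.** An ECG is paired if it can fall inside its own window and also within the 15 minutes before a PK draw that is inside its window.

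| Part | Day | PK times that day | ECG times paired |
|---|---|---|---|
| Escalation | C1D1 | pre-dose, 0.25, 0.5, 1, 2, 3, 4, 6, 8 h (12 h if available) | 5 of 5 |
| Escalation | C2D1 | pre-dose only | 1 of 5 |
| Expansion, Phase II | C1D1 | pre-dose, 2, 4, 6, 8, 24 h | 3 of 5 (pre-dose, 4, 8 h) |
| Expansion, Phase II | C2D1 | none | 0 of 5 |

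Over both days, escalation pairs 5 + 1 = 6 of 10 and expansion or Phase II pairs 3 + 0 = 3 of 10. No post-dose ECG on C2D1 is paired in any part of the study.

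**Can the windows rescue the C1D1 mismatches in expansion and Phase II?**
- 1 h ECG: latest time 80 min. The 2 h draw is earliest at 120 - 10 = 110 min, so its ECG is earliest at 110 - 15 = 95 min. The gap is 15 min.
- 3 h ECG: latest time 210 min. The 4 h draw is earliest at 240 - 10 = 230 min, so its ECG is earliest at 215 min. The gap is 5 min. The 2 h draw is over by 130 min, before the 3 h ECG window opens at 150 min.

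Neither can be paired.

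**Is C1D15 at steady state?** Protocol 2.3 gives a half-life of 8.42 to 10.9 h. Five half-lives are 42.1 to 54.5 h, against 14 × 24 = 336 h of dosing before C1D15. As a harsher check, a fourfold accumulation under once-daily dosing and linear kinetics would imply an effective half-life of 24 × ln 2 / ln(4/3) = 57.8 h. Five of those are 289 h, still under 336 h. C1D15 therefore serves as a steady-state day.

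**Effect of moving the second series to C1D15, with ECG times unchanged.** Escalation pairs 5 of 5 on that day (four post-dose). Expansion and Phase II pair 3 of 5 (two post-dose, 4 and 8 h), so there the times must be aligned as well as the day.

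**The SAP's Day 22.** One pre-dose sample in escalation, and none elsewhere, cannot give the parameters in the SAP's PK table. Its terminal rate constant alone needs at least three points.

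**The case against.** A reader might infer that the study yields no paired QTc and post-dose concentration at steady state. The documents do not support that. Table 7-1 marks an ECG on C1D15, which has pre-dose and post-dose PK samples in every part, so a pair is possible there. Because the time is not stated, it is not assured. Escalation also gives a trough pair on C2D1.

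A reader might also infer that the ECG safety endpoint is compromised. It is not. Serial post-dose ECGs at steady state are still recorded on C2D1, the planned summaries are descriptive, and neither document describes a concentration-QTc analysis. In escalation, concentrations at the same post-dose times are available from the same patient one week before, on C1D15. These are an imperfect substitute for concurrent samples, but they are data.

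The risk evidence is mixed. The dog study reports no change in corrected QT at doses up to 100 mg/kg (1.2.1.1.3), and 1.2.2 reports no significant cardiotoxicity in the clinical data so far. SAP section 7 adds that the programme was stopped early, which limits the practical reach, above all for Phase II.

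These arguments limit the consequence but do not remove the contradiction. The permission to modify time points does not cure it either: the protocol reports human PK from 22 patients as of 18 January 2022, and the current text keeps the mismatch.

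**Conclusion.** The pairing rule is wrong as written. It fails for 4 of 5 ECG times on C2D1 in escalation, 5 of 5 on C2D1 in expansion and Phase II, and 2 of 5 on C1D1 in expansion and Phase II. It can be met on C1D1 in escalation, at pre-dose on C2D1 in escalation, and at three C1D1 times in expansion and Phase II. No serial, time-specified post-dose pairs are scheduled at steady state in any part of the study.

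This is an internal inconsistency that should be corrected. It does not invalidate a planned analysis. The counts rest on the sampling tables and windows as printed. The statement about steady state rests on the protocol's reported half-life and accumulation.

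**What to change.** Reconcile Protocol 7.2.1.7 with Tables 7-1 to 7-3, and settle one steady-state PK day for Protocol 10.6.4 and SAP 8.9. Moving the ECGs alone would leave the two documents in conflict.

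**Simplest route.** Place the second serial ECG set on C1D15 and keep the routine ECG on C2D1. In expansion and Phase II, set the ECG times to the Table 7-3 PK times on both days. Change SAP 8.9 from Day 22 to C1D15. Escalation then pairs 10 of 10 with no extra blood draw, and patients are already being sampled to 8 hours on C1D15. If the routine ECG is a single tracing, the total over C1D1, C1D15 and C2D1 stays at 11 (5 + 1 + 5 now, 5 + 5 + 1 after). C1D15 also lies inside the 21-day DLT period, and Day 22 does not.

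**Cost.** There are fewer serial ECGs on C2D1. In expansion and Phase II the 1 h and 3 h ECGs are replaced. Taking all six Table 7-3 times gives six ECGs per day against five now; leaving out 24 h keeps five. Footnote 10 of Table 7-1 omits the 24 h sample that Table 7-3 includes, so that should be settled at the same time.

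**Alternative.** The sponsor may instead add C2D1 PK samples: four in escalation (4 × 2 mL = 8 mL) and five in expansion and Phase II (5 × 2 mL = 10 mL). That pairs 5 of 5 on C2D1, but the 1 h and 3 h gaps on C1D1 in expansion and Phase II would still need correcting.

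For data already collected, the report should state which ECGs have a matched sample and that serial steady-state pairs were not scheduled.
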